8. RESEARCH METHODS

8.1 STUDY DESIGN

This is a national, multicenter, non-interventional, observational, cohort study based on newly collected data with an observational period of at least 8 weeks until switch or discontinuation of Spiriva® Respimat® treatment or up to 52 weeks after baseline visit whatever occurs first.

This NIS is designed as single-arm study without a specific comparator in a parallel arm. All included patients must have been on treatment with Spiriva® HandiHaler® for at least 6 weeks prior to study inclusion. Therefore, patient could serve as their own control (baseline values) and a parallel arm being on Spiriva® HandiHaler® is not obligatory to address the primary objective of the NIS.

The study is non-interventional on the therapeutic strategy as the decision to switch the patient from Spiriva® HandiHaler® to Spiriva® Respimat® device is made by the treating physician prior to study inclusion due to patient's individual needs. Patients will be treated within clinical routine practice and according to the current standard of care to assess the real-world situation in Swiss clinical practice. The patients included in the study will be followed for 1 year (approximately 52 weeks) after switching to the Respimat® device with no fixed study visit schedule. The treating physician will be asked to record data for study endpoint assessments in week 8 after baseline to assess therapeutic success of the switch to the Respimat® device. Patients who discontinued Spiriva® Respimat® treatment or who were switched to another treatment will be asked to perform an end-of-treatment (EoT) visit (= follow-up visit).

This national study will be conducted as a multicenter study to collect information on current status, and characteristics of patients switching from HandiHaler® to Respimat® device from

various sites to achieve balanced data with regard to geographic distribution, type of clinical setting (e.g., academic versus community health centers), and prescriber specialty which are representative for the larger patient and prescriber community.

8.2 SETTING

8.2.1 Study sites

It is planned that data of approximately 225 patients from approximately 40 sites will be collected. Site selection will be performed to reflect routine COPD care to secure representativeness of the Swiss COPD population. As described in section study design, achievement of balanced data regarding geographic distribution, type of clinical setting (e.g., academic versus community health centers), and prescriber specialty which are representative for the larger patient and prescriber community will be considered for site selection.

A log of all patients included into the study (i. e., having given informed consent form) will be maintained in the investigator's site file at the investigational site irrespective of whether they have been switched or not.

8.2.2 Study population

Patients will be enrolled consecutively in the study. The decision to switch the patient from Spiriva® HandiHaler® to Spiriva® Respimat® will be made by the treating physician to the patient's need and to the standard of best medical practice prior to the inclusion into the study.

Patients with COPD planned to be switched according to the respective SmPC and consenting to participate in the study are eligible. To avoid any selection bias, all eligible patients will be invited to participate in this study, in the order in which their eligibility is determined. A time window of 1 years is foreseen for recruitment of the patients. Patients will be treated within clinical routine practice and according to the current standard of care. Patients who discontinue from treatment before the visit at week 52 will be asked to complete an EoT visit.

Inclusion criteria:

Patients can be included if all following criteria are met:

- Participants ≥ 40 years of age at baseline visit
- Patients with confirmed diagnosis of COPD*
- Patients who have been on Spiriva® HandiHaler® for ≥ 6 weeks at baseline visit
- Patients for whom a switch from Spiriva® HandiHaler® to Spiriva® Respimat® was planned prior to study inclusion. If additional inhalative COPD drugs (AICDs) are

used: AICD treatment must have been stable for at least 6 weeks before study inclusion

- Signed written informed consent form to participation

*Confirmed by spirometry: FEV1/FVC <0.7 (last available FEV1 and FVC including % predicted)

Exclusion criteria:

- Patients who have contraindications to Spiriva® Respimat® according to the current prescribing information label/ summary of product characteristics (SmPC)
- Patients who have signs of a current, acute respiratory tract infection 2 weeks prior visit 1
- Patients for whom further follow-up will not be possible at the enrolling site during the planned observational period (of approximately 8 weeks)
- Patients with confirmed diagnosis of only asthma
- Patients who had > 1 moderate to severe exacerbation(s) within the last 6 weeks prior to study inclusion
- Patients who are pregnant or breastfeeding
- Patients participating in an ongoing interventional study

8.2.3 Study visits

Eligible patients who sign the informed consent form (ICF) will undergo the baseline visit.

Patients will be followed up over an observational period of approximately 52 weeks after baseline visit (visit 1). During the observational period, 2 further visits will be performed. Visit 2 will be approximately in week 8, visit 3 will be performed in week 52 as follow-up visit.

Patients who discontinue from the treatment before the visit at week 52 will be asked to complete an EoT visit.

[Figure 8.2.3:1](#) provides a study flow chart. [Table 8.2.3:1](#) gives an overview about the parameters collected during the study.

Figure 8.2.3:1 Study flow chart.

[figure not shown]

Table 8.2.3:1 Data collection parameters

Parameter	Baseline visit (Visit 1)	Visit 2 (approx. 8 weeks after baseline visit)	Visit 3 (approx. 52 weeks after baseline visit)/EoT visit (if Spiriva® Respimat® treatment is discontinued or switched)
Informed Consent Form	X		
Inclusion / Exclusion criteria	X		
Patient demographics (age [years], gender [m/f/d], height [cm], and weight [kg])	X		
Start of COPD (age at onset [years])	X		
Concomitant diseases / comorbidities (relevant comorbidities such as cardiovascular diseases, diabetes mellitus type 2, depression and diseases affecting the preparing and handling of the Respimat® device)	X		
Start of inhalative bronchodilators for COPD treatment [year]	X		
Concomitant COPD medication including additional inhalative COPD drugs (AICDs, dosage, date of onset [day-month-year]) up to 6 weeks before baseline visit	X		
Changes in COPD treatment scheme (date [day-month-year], reason(s))		X	X
Reason(s) for change from Spiriva® HandiHaler® to Spiriva® Respimat®	X		
Number of moderate to severe exacerbations in the last 12 months	X		
Number of exacerbations leading to hospitalization in the last 12 months	X		
mMRC breathlessness scale, completed by the patient	X	X	
Last available FEV1 and FVC (value and date measured [day-month-year])	X		
Respimat® training (yes/no)	X		

COPD severity based on GOLD assessment ¹	X		
GOLD spirometric classification, if available ²	X		
Smoking status [never/former/current]/history [number of pack years]	X		
Health and functional status by CCQ questionnaire, completed by patient	X	X	
[REDACTED]	■	■	
[REDACTED]	■	■	
Safety: Adverse Drug Reactions (serious and non-serious), fatal AE, pregnancy		X	X
Assessment of treatment start [yes/no], date of onset of treatment [day-month-year]		X	
[REDACTED]	■		
[REDACTED]	■		
Rationale for Spiriva® Respimat® treatment discontinuation (if applicable)		X	X
Continuation or discontinuation of treatment with Spiriva® Respimat® after the study [yes/no]/date [day-month-year]		X	X

¹ GOLD patient group (B, C or D) will be automatically calculated based on available exacerbation history and mMRC.

² GOLD stage 1-4 spirometric classification of airflow limitation based on post-bronchodilator FEV1 and FVC.

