Study design:	Open label, observational, non-interventional, national, multicenter study including COPD patients ≥ 40 years switching from Spiriva® HandiHaler® to Spiriva® Respimat® with an observational period of approximately 8 weeks (which is the average time between medical consultations). Patients will be followed-up to either discontinuation of Spiriva® Respimat® or up to week 52, whatever occurs first.
Population:	
COPD patients ≥ 40 years who are planned to be switched from Spiriva® HandiHaler® to Spiriva® Respimat®.
 
The decision to switch is made by the treating physician and patient according to patient's need and to the standard of best medical practice. This decision is made independently and prior to inclusion in this NIS.
 
Patients who will undergo a switch from Spiriva® HandiHaler® to Spiriva® Respimat® will be informed about the scope of the study and asked whether they would like to participate.

	
Inclusion criteria:
 
 Participants ≥ 40 years of age at baseline visit Patients with confirmed diagnosis of COPD* Patients who have been on Spiriva® HandiHaler® for ≥ 6 weeks at baseline visit Patients for whom a switch from Spiriva® HandiHaler® to Spiriva® Respimat® was planned prior to study inclusion. If additional inhalative COPD drugs (AICDs) are used: AICD treatment must have been stable for at least 6 weeks before study inclusion Signed written informed consent form to participation 
*Confirmed by spirometry: FEV1/FVC <0.7, (last available FEV1 and FVC including % predicted)
 
Exclusion criteria:
 
 Patients who have contraindications to Spiriva® Respimat® according to the current prescribing information label/ summary of product characteristics (SmPCs) Patients who have signs of a current, acute respiratory tract infection 2 weeks prior visit 1 Patients for whom further follow-up will not be possible at the enrolling site during the planned observational period (of approximately 8 weeks) Patients with confirmed diagnosis of only asthma Patients who had > 1 moderate to severe exacerbation(s) within the last 6 weeks prior to study inclusion Patients who are pregnant or breastfeeding Patients participating in an ongoing interventional study

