Variables:	
Eligible patients who signed the informed consent form will undergo the baseline visit (= visit 1).
 
Visits are to be scheduled as per standard-of-care. Documentation at the sites is planned at baseline (month 0, visit 1) and after approximately 8 weeks after treatment start (visit 2). Patients will be requested to have an End-of Treatment (EoT) visit (Follow-up visit) if they discontinue Spiriva® Respimat® treatment or if they switch to another inhalative medication. Patients who are still on Spiriva® Respimat® will have a follow-up visit (visit 3) approximately 52 weeks after baseline visit. It is planned that each patient will have 3 visits during the 1-year observational period. Additional visits may be performed as needed, such as when COPD treatment requires adjustment, or whenever otherwise deemed necessary by the study physician based on usual care.

	Main data collected:
	
At baseline (visit 1):
 
• Patient demographics (age, gender, height, weight)• Concomitant diseases / comorbidities (relevant comorbidities such as cardiovascular diseases, diabetes mellitus type 2, depression, and diseases affecting the preparing and handling of the device)• Date of confirmed COPD diagnosis• Start with inhalative bronchodilators for COPD treatment [year]• Concomitant COPD medication including additional inhalative COPD drugs (AICDs, dosage, date of onset)• Breathlessness based on mMRC score• Last available FEV1 and FVC including % predicted (value and date measured, closest to the date of baseline visit)• Exacerbation history (number of moderate-to-severe exacerbations in the last 12 months before study inclusion, hospitalizations required)• Smoking history (number of pack years) and status (never, former, current) 
[REDACTED]
 
[REDACTED]
 
[REDACTED]
 
[REDACTED]

	
At visit 2:

	
• Breathlessness based on mMRC score
	
[REDACTED]

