	
 CCQ score and the CCQ symptom, mental state, and functional state domain scores 
■ [REDACTED]
 
■ [REDACTED]
 
■ [REDACTED]
 
■ [REDACTED]
 
■ [REDACTED]
 
■ [REDACTED]
 
 Safety; ADR (serious and non-serious), fatal AEs, pregnancies 
At visit 3:
 
 Changes in COPD treatment scheme (yes/no, date, reason(s), kind of new treatment) Discontinuation of Spiriva® Respimat® treatment (date, reason(s)) Safety; ADR (serious and non-serious), fatal AEs, pregnancies (including exacerbations)
Data sources:	
To be completed by the physician:
 
 Patient demographics Patient medical files 
■ [REDACTED]
 
■ [REDACTED]
 
■ [REDACTED]
 
■ [REDACTED]
 
To be completed by the patient:
 
 mMRC breathlessness scale at baseline (visit 1) and visit 2 Health and functional status by CCQ at baseline (visit 1) and visit 2 
■ [REDACTED]

Study size:	
Primary endpoint:
 
Assuming 40% of high CCQ score patients have a 0.2 improvement in CCQ score from baseline at 8 weeks on treatment, then with a sample size of 100, the 95% CI for the response rate will be (0.304, 0.49)6.
 
Secondary endpoint:
 
Assuming 30% of all patients have a 0.2 improvement in CCQ score from baseline at 8 weeks on treatment, then with a total sample size of 200, the 95% CI for the response rate will be (0.236, 0.364).
 
With a dropout rate of 10% we would need a total of about 225 patients.

	
Sample size assumes that Respimat® is better compared to HandiHaler®. The sample size calculation/justification can only provide a rough estimate of the statistical power in such an exploratory real-world setting. Recruitment will continue until the minimum sample size is achieved.

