8.7 DATA ANALYSIS

This section provides specifications for the preparation of the final statistical analysis plan (SAP), which will be issued prior to database lock. Any differences compared to this statistical section should be identified and documented in the final SAP.

The following data handling conventions will be followed:

- Baseline assessments are those that were completed at the baseline visit (visit 1).
- The following analysis time windows will be utilized in the analysis:
 - Assessments scheduled to be done:
 - Approximately 8 weeks after treatment start (= visit 2): 8 weeks \pm 2 weeks
 - Approximately 52 weeks after treatment start (= visit 3, follow-up visit): 52 weeks \pm 4 weeks
 - If patients discontinue or switched from Spiriva® Respimat® treatment, they will be asked to perform an EoT visit (= visit 3) nearby to the date of stopping Spiriva® Respimat® treatment

No formal hypothesis testing will be performed since this is a self-controlled study. The analysis of the data will be of descriptive and explorative character. Variables will be summarized using appropriate statistical methods

The statistical characteristics presented in the end-of-text tables will be N / mean / SD / min / median / max for continuous variables. Tabulations of relative and absolute frequencies will be presented for categorical variables. Proportions and 95% CI will be given when appropriate.

At baseline, the following data will be collected as available in routine clinical practice:

Patient demographics and medical history:

- Patient demographics (gender, age, height, weight)
- Comorbidities (main diagnosis and concurrent diagnosis according to MedDRA, version valid at the time of database closure)
- COPD related concomitant medication (according to the WHO classification, version valid at the time of database closure)
- Details of treatment with inhaled respiratory agents before the study
- History of smoking
- GOLD spirometric classifications (1, 2, 3, 4) and GOLD patient groups (A, B, C, D), date of confirmed COPD diagnosis

Data collection at baseline:

- Breathlessness based on mMRC score at visit 1; secondary endpoint

- CCQ score and CCQ symptom, mental state, and functional state scores; secondary endpoint

■ [REDACTED]

■ [REDACTED]

■ [REDACTED]

The following data will be collected as available in routine clinical practice at visit 2:

- Assessment of treatment start with date of onset, if applicable

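### For a patient who stops Respimat before week 8, the protocol does not settle whether visit 2, the only post-switch CCQ, still takes place, and the end-of-treatment visit collects no CCQ

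*Combined protocol and SAP*

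**What the plan says.** **What is collected.** Table 8.2.3:1 in Section 8.2.3 marks "Health and functional status by CCQ questionnaire, completed by patient" at baseline and visit 2, with nothing under visit 3/EoT. The abstract's data sources agree: "Health and functional status by CCQ at baseline (visit 1) and visit 2". The mMRC row follows the same pattern. Treatment start (yes/no and date) is asked at visit 2 only (Table 8.2.3:1, Section 8.4). The visit 3/EoT data list in Section 8.7 contains none of the three. These rows are legible, so redaction does not explain the blanks.

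**What the primary outcome needs.** Sections 8.3.2.1 and 8.7.1 define improvement as a fall in CCQ of at least 0.2 from baseline to visit 2, in patients with baseline CCQ of 2 or more.

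**What happens after stopping.** The abstract's study design says "Patients will be followed-up to either discontinuation of Spiriva® Respimat® or up to week 52, whatever occurs first". Section 8.7 says of patients who stop or switch that "they will be asked to perform an EoT visit (= visit 3) nearby to the date of stopping Spiriva® Respimat® treatment". Section 8.2.3, however, says "During the observational period, 2 further visits will be performed", and the abstract says "It is planned that each patient will have 3 visits during the 1-year observational period". The abstract's milestones give an individual observation period of at least 8 weeks.

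**Timing.** Section 8.7 sets the window as "Approximately 8 weeks after treatment start (= visit 2): 8 weeks", plus or minus 2 weeks. The abstract adds "Visits are to be scheduled as per standard-of-care".

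**The concern.** The study asks whether patients benefit from changing device. Those who give up the new device within 8 weeks bear directly on that question, and they are the patients whose only post-switch CCQ is in doubt. If they are not measured and improve less often than the rest, the observed rate overstates the benefit. If they improve equally often, it does not.

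The analysis plan can decide how a missing score is counted, but it cannot recover a questionnaire that was never handed out. Section 8.2.1 plans about 40 sites, and each would have to interpret the visit rules for itself. A patient seen only at an EoT visit would also have no recorded treatment start, although the visit 2 window is counted from it.

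**Working it through.** **Step 1. The passages side by side, for a patient who stops in, say, week 4.**

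| Place | What it implies about visit 2 |
|---|---|
| Abstract, study design | Follow-up ends at discontinuation: no visit 2 |
| Section 8.7, time windows | EoT visit counts as visit 3, near the stop date: suggests visit 1, then visit 3 |
| Abstract, variables | Three visits planned per patient: visit 2 takes place |
| Abstract, milestones | At least 8 weeks of observation: visit 2 takes place |
| Section 8.2.3, text | Two further visits, with no condition on treatment: visit 2 takes place |
| Table 8.2.3:1 and Section 8.7, visit 2 items | Reasons for stopping are collected at visit 2: it can follow a stop |
| Section 8.1 | One sentence sets a minimum of 8 weeks and also an end at switch or discontinuation if that comes first |

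The conflict is by implication. No sentence cancels visit 2 for an early stopper, and none confirms it. If visit 2 has not yet been held, an EoT visit in weeks 6 to 10 falls inside the visit 2 window, and no passage says which form is then completed.

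**Step 2. Reproduce the plan's figures (Section 8.5).**
- Primary: 0.40 ± 1.96 × √(0.40 × 0.60 / 100) = 0.40 ± 0.096, or 0.304 to 0.496. This matches.
- Secondary: 0.30 ± 1.96 × √(0.30 × 0.70 / 200) = 0.2365 to 0.3635. This matches the stated 0.236 to 0.364 to rounding.
- Total: 200 / 0.90 = 222.2, so 223, against about 225 stated. This is consistent.

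**Step 3. Size of the possible effect.** High-CCQ patients enrolled: 225 × 0.5 = 112.5, taken as 112 for the intervals. This assumes that every enrolled patient starts Respimat. Let m be the share without a visit 2 CCQ and r their unknown improvement rate, with 40% improving among those measured:

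rate over all = (1 − m) × 0.40 + m × r.

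The protocol gives no early-stop share, so m is an assumption. The bounds take r = 0 and r = 1.

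| m | Patients | r = 0 (95% CI) | r = 1 (95% CI) |
|---|---|---|---|
| 2% | 2.25 | 39.2% (0.302 to 0.482) | 41.2% (0.321 to 0.503) |
| 5% | 5.6 | 38% (0.290 to 0.470) | 43% (0.338 to 0.522) |
| 10% | 11.25 | 36% (0.271 to 0.449) | 46% (0.368 to 0.552) |

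Each 1% missing lowers the worst case by 0.4 points and raises the best case by 0.6. The 10% row equals the whole planned dropout and is an outer bound, since that dropout may include losses that an EoT questionnaire would not recover.

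For the secondary rate of 30% on 225 patients, (1 − m) × 0.30 + m × r gives 29.4% to 31.4%, 28.5% to 33.5%, and 27% to 37%.

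**Step 4. Compare with the planned precision.** The largest downward shift is 4 points, against a half-width of 9.6. A downward shift of 9.6 points would need m = 0.096 / 0.40 = 24% missing.

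**The case against.** The best counter-reading is that visit 2 was always meant for everyone. The EoT visit is equated with visit 3, never with visit 2. The abstract first states an observation period of about 8 weeks and then speaks of follow-up to discontinuation, which can be read as the phase after visit 2. Section 8.1 asks physicians to record endpoint data in week 8, and Section 8.2.2 excludes patients who cannot be followed at the site over those 8 weeks. This is a fair reading and may be the intended one. A reader might infer that the protocol drops visit 2 for early stoppers, but the text does not go that far. What remains is that a site could reasonably follow either reading. The flow chart, which might settle it, is not reproduced in the text available here.

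A reader might also infer that standard-of-care scheduling would push the next visit of an early stopper beyond the window. That would treat the mean 8-week interval in Section 6.5 as fixed and assume that an EoT visit resets it. The documents say neither, and the abstract allows additional visits.

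The objectives concern about 8 weeks of treatment, and Section 8.5 words its assumption as on treatment. A CCQ from week 2 or 3 does not measure that, so leaving it off the EoT form is defensible for the main rate. It does not make the score worthless. The CCQ covers the previous 7 days (Sections 3 and 6.3), so one completed close to the stop date largely describes the Respimat period. If the EoT visit comes later, the score may partly reflect another inhaler.

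Finally, missing-data rules and the list of protocol deviations are deferred to an analysis plan due before database lock (Sections 7, 8.7 and 8.10.4). Their absence here is not an error. Collection has to be settled before the visits take place.

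**Conclusion.** The point holds as a gap in data collection. Visit 2 is the only post-switch source of the CCQ, mMRC and treatment start. The passages conflict by implication on whether an early stopper attends it, and no rule covers an EoT visit inside the visit 2 window.

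It would go too far to say that the primary rate is biased upwards. The protocol gives neither the share of early stoppers nor their expected improvement rate, so the direction is unproven. Under assumed missing shares of 2% to 10%, the planned 40% could fall by 0.8 to 4 points or rise by 1.2 to 6, all within the planned half-width of 9.6. Section 8.7 plans no formal test, so no decision threshold depends on the result. A confidence interval does not, however, cover loss that is related to outcome. The case for acting is that the data cannot be recovered later and cost little to collect. Minor to moderate priority.

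**What to change.** 1. Reconcile the abstract (study design, variables, milestones) with Sections 8.1, 8.2.3 (including Table 8.2.3:1) and 8.7. State that visit 2 data (CCQ, mMRC, treatment start) are sought at week 8 whether or not Respimat is continued, and that an EoT visit inside the 8 ± 2 week window also completes the visit 2 form if visit 2 has not yet been held.
2. Add the CCQ, mMRC and treatment-start field to any EoT visit that occurs before visit 2.
3. In the analysis plan, say whether a week 8 CCQ taken after stopping counts in the main rate. Keep the observed visit 2 rate as the main result. Pre-specify two sensitivity rates over all patients with baseline CCQ of 2 or more who started Respimat: one counts a missing visit 2 CCQ as not improved, and the other uses the EoT CCQ where visit 2 is missing. Give a rule for patients whose treatment start was never recorded.
4. When protocol deviations are listed under Section 8.10.4, state that an early stop or a missing visit 2 CCQ does not by itself remove a patient from the full analysis set.

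**Cost.** A 10-item questionnaire that Section 6.3 describes as taking only minutes, the mMRC and one start field at a visit already requested; possibly an extra week 8 contact at some sites; and a few lines of text. The sensitivity rate that counts missing as not improved may come out a few points below the main one.
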